7.1.3.3 Copeptin

Blood samples for exploratory analysis of copeptin levels in plasma will be collected at Visit 2, Visit 4 and Visit 8. The biomarker copeptin can be easily tested for, and is therefore used as an AVP surrogate to potentially identify low nocturnal vasopressin levels in plasma. In patients with NP, an inverse circadian rhythm of vasopressin is suspected, resulting in low nocturnal concentrations, which may be the root cause of NP. Copeptin may be a useful biomarker to diagnose NP due to low levels of endogenous AVP, thereby identifying the ideal candidate for antidiuretic therapy (Brunell, 2016) and consequently treatment with FE 201836.

7.1.4 Vital Signs

Diastolic and systolic blood pressure (mm Hg) and heart rate (beats per minute) will be measured after resting for 5 minutes in a sitting position, according to usual clinical practice at all trial visits.

Measurements outside normal ranges will be assessed by the investigator as 'abnormal, not clinically significant' or 'abnormal, clinically significant'. Any abnormal, clinically significant changes should be reported as adverse events.

7.1.5 24-Hour Urine Volume and Nocturnal Urine Volume

Data on 24-hour urine volume, i.e., including NUV, will be obtained from the 3-day voiding diary (Section 7.1.1.1) completed prior to Visits 2, 4, 5 and 8. In addition, NUV data will be obtained from the 3-day voiding diary completed prior to Visit 3 (Table 7-1).

7.2 Other Assessments

7.2.1 Demographics

Demographic data, including date of birth and race, will be collected at screening (Visit 1).

7.2.2 Medical History

Information on clinically significant previous and concomitant illnesses, signs or findings from assessments and examinations during the screening, including surgical history, will be recorded as medical history at the screening visit (Visit 1).

7.2.3 Concomitant Medication

Information on concomitant medications will be collected at each visit throughout the trial, as described in Section 4.3.1. Concomitant medications are defined as any medication, other than the IMP, taken by the subject at entry and during the trial. Prohibited medications/therapies are listed in Section 4.3.2.

7.2.4 Body Weight and Height

Body weight and height will be measured to calculate the body mass index (BMI). The eCRF will be configured to automatically calculate the BMI. Height (without shoes) will be measured at screening (Visit 1).

Body weight (without overcoat and shoes) will be measured at all visits. The same scale should preferably be used on the subject during the course of the trial for consistency in readings.

If the subject has gained more than 2 kilograms between trial visits, the serum sodium level must be measured, as described in Section 7.1.3.1.

7.2.5 Physical Examination

Physical examinations will be performed at Visits 1, 4 and 8 by the investigator or a delegated sub-investigator (MD, Medical Doctor; DO, Doctor of Osteopathic Medicine; PA, Physician Assistant; NP, Nurse Practitioner) and must not be delegated to any other trial site personnel. The same individual should preferably perform the physical examinations for a subject for consistency in evaluation.

A complete physical examination will include, at a minimum, assessments of the cardiovascular, respiratory, gastrointestinal, urological and neurological systems. Any abnormal, clinically significant changes should be reported as adverse events.

7.2.6 Pregnancy Test

A serum pregnancy test will be performed in all pre- and peri-menopausal female subjects at screening (Visit 1), Visit 4 and at the end-of-trial visit (Visit 8). A urine pregnancy test will also be performed at screening (Visit 1).

Female subjects of childbearing potential must have documentation of an acceptable effective method of contraception, as described in Section 4.3.4. Amenorrhea of >12 months duration based on the reported date of the last menstrual period is sufficient documentation of post-menopausal status and does not require a pregnancy test.

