4.1.2 Exclusion Criteria

Any subject meeting one or more of the following exclusion criteria between Visit 1 (screening) through Visit 4 (randomisation) will be considered as a screening failure:

1. Current diagnosis of Obstructive Sleep Apnoea (OSA)
2. Restless Legs Syndrome (RLS)
3. Bladder Outlet Obstruction (BOO) or urine flow <5 mL/s, as confirmed by uroflowmetry upon suspicion during screening prior to Visit 2
4. Urinary incontinence defined as an average of >1 episode/day in the 3-day e-Diary prior to Visit 2 (occasional urge incontinence during daytime or at night on the way to void is not necessarily exclusionary)
5. ^c
6. Any pelvic or lower urinary tract surgery and/or radio therapy or previous pelvic irradiation within the past 6 months prior to Visit 1. Including e.g., transurethral resection for BOO or BPH, hysterectomy or female incontinence procedures
7. Genito-urinary tract pathology that can in the investigator's opinion be responsible for urgency or urinary incontinence e.g., symptomatic or recurrent urinary tract infections, interstitial cystitis, bladder-related pain, chronic pelvic pain syndrome, or stone in the bladder or urethra causing symptoms
8. A history of cancer with the last date of disease activity/presence of malignancy within the last 12 months prior to Visit 1, except for adequately treated basal cell carcinoma of the skin
9. History of any neurological disease affecting bladder function or muscle strength (e.g., Multiple Sclerosis, Parkinson's, spinal cord injury, spina bifida)
10. Habitual (fluid intake >3L per day) or psychogenic polydipsia
11. Uncontrolled hypertension, as judged by the investigator
12. ^a
13. Uncontrolled diabetes mellitus, as judged by the investigator
14. Central or nephrogenic diabetes insipidus
15. Known history of Syndrome of Inappropriate Antidiuretic Hormone (SIADH) secretion
16. History of gastric retention
17. Suspicion or evidence of congestive heart failure, (New York Heart Association [NYHA] class II, III, IV)

^c Original exclusion criterion omitted as per Clinical Trial Protocol Amendment 03 (applicable for all trial sites).

^a Original exclusion criterion omitted as per Clinical Trial Protocol Amendment 01 (applicable for all trial sites).

18. Hyponatraemia:

- Serum sodium level <135 mmol/L at Visit 1 (re-tested, with results available within 7 days)
- Serum sodium level <130 mmol/L at Visit 3 (re-tested, with results available within 7 days)

19. Hepatic and/or biliary diseases:

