
- Child-Pugh Class A, B, or C
or
- Aspartate aminotransferase and/or alanine aminotransferase levels >3x the upper limit of normal range as well as total bilirubin level >2x the upper limit of normal range

20. Known history of hypersensitivity to desmopressin ODT

21. Pregnancy, breastfeeding, or a planning to become pregnant during the period of the trial

22. Known alcohol or substance abuse

23. Work or lifestyle that may interfere with regular night-time sleep e.g., shift workers

24. Any other medical condition, laboratory abnormality, psychiatric condition, mental incapacity, or language barrier that, in the judgment of the investigator, would impair participation in the trial

25. ^d

26. Previous participation in a nocturia, Benign Prostatic Obstruction (BPO), or OAB clinical trial within the past 6 months prior to Visit 1

27. The subject is in a state of dependence of the sponsor, or is directly or indirectly involved in the conduct of this trial as an investigator, sub-investigator, trial coordinator or other trial staff member, or the subject is a first degree family member, significant other or relative residing with one of the above persons involved directly or indirectly with the trial

28. Use of any restricted therapy not in accordance with the protocol

29. Use of any prohibited therapy listed below:

- Current or former (within 3 months prior to screening) treatment with any other IMP
- Unstable electrostimulation or behavioural bladder training program less than 3 months prior to screening (stable electrostimulation or behavioural bladder training program started at least 3 months before screening are acceptable)
- Thiazide diuretics
- Antiarrhythmic agents
- V₂-receptor antagonists/agonists (e.g., vaptans/desmopressin, vasopressin)
- Loperamide

^d Original exclusion criterion omitted as per Clinical Trial Protocol Amendment 03 (applicable for all trial sites).

- Botulinum toxin (cosmetic non-urological use is acceptable)
- Valproate

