5.6 Treatment Compliance

5.6.1 Dispensing and Accountability

The IMP will be handled by authorised personnel at the trial site according to instructions provided by the sponsor.

The IMP for the active run-in will only be dispensed to subjects who meet the eligibility criteria at Visit 2.

The IMP for the randomised treatment period will only be dispensed to subjects who meet the eligibility criteria at Visit 4 and are randomised into the trial.

The investigator (or his/her designee) will maintain a Drug Dispensing Log detailing the dates and quantities of IMP dispensed to, and used by each subject, as well as the batch number(s).

Each subject should return all unused and used IMP bottles and ODT blister sheets (empty foils) to the trial site. The delegated designee at each trial site will reconcile all used and unused IMP and maintain all IMP (including empty bottles and ODT blister/foils) for drug accountability. The monitor will verify the drug accountability during the trial.

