6.1 Trial Flow Chart

The overall trial design is shown in Section 3.1. The assessments scheduled for each visit are presented in the flow chart in Section 6.1, listed in Sections 6.2 to 6.7 and further described in Section 7.

Table 6-1 Trial Flow Chart

Assessment	Screening/ Lifestyle Changes		Active Run-in Period		Washout Period	Randomised Trial Period					
	Visit (V)	V1	Reminder	V2	Telephone Follow-up	V3	V4 ^L	V5	V6	V7	V8 ^O
Week								1	4	8	12
Day/Visit window		S1		-14	-10±1 ^m	-7 ⁿ	1	8±2	28±3	56±3	84±7
Informed consent	X										
Inclusion and exclusion criteria	X			X		X	X				
Lifestyle Changes ^a	X	X		X	X	X	X	X	X	X	
Randomisation							X				
Dispense e-Diary	X										
e-Diary Training	X		^b								
e-Diary Compliance				X		X	X	X	X	X	X
Dispense IMP				X			X	X	X	X	
Accountability of IMP						X		X	X	X	X
Demographics	X										
Medical history	X										
Physical examination	X						X				X
Body weight	X			X		X	X	X	X	X	X
Height	X										
Vital Signs ^c	X			X		X	X	X	X	X	X
Electrocardiogram (ECG)	X										X
Pregnancy test - serum ^d	X						X				X
Pregnancy test - urine ^d	X										
Clinical chemistry, haematology, urinalysis	X						X	X	X	X	X
Coagulation factors	X						X		X		X
Copeptin				X			X				X
OSA assessment ^e	X										
Serum sodium ^p	X ^j					X ^{k,n}		X	X	X	X
Voiding Diary ^f				X		X	X	X	X	X	X
NI Diary ^f				X			X	X	X	X	X
PGI-S ^g				X			X	X	X	X	X
PGI-I ^g								X	X	X	X
ISI ^h				X			X		X	X	X
Bother ^h							X	X	X	X	X
Exit Interview ⁱ											X
Adverse events				X	X	X	X	X	X	X	X
Concomitant medication	X			X		X	X	X	X	X	X

- Subjects will be reminded about lifestyle changes throughout the trial.
- Original footnote omitted as per Clinical Trial Protocol Amendment 03 (applicable for all trial sites).
- Vital signs (blood pressure and heart rate) measured after resting for 5 minutes in a sitting position.
- Applicable to all pre- and perimenopausal female subjects.
- Original footnote omitted as per Clinical Trial Protocol Amendment 03 (applicable for all trial sites).
- Completed by the subjects at home over 3 consecutive days just prior to scheduled visits.
- Completed at home 1 day prior to scheduled visits.
- Completed at the site visit before any consultation with the trial site personnel takes place.
- A sample of subjects (at trial sites in the USA) who completed the trial will be invited to participate, by telephone, in an exit interview within 14 days of attending Visit 8.

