6.2 Visit 1 Screening

Potential participants will be scheduled to come to the clinic for the screening assessments.

The following must take place during the screening period:

- Signing of informed consent
- Allocation of a screening number
- Inclusion and exclusion criteria will be evaluated.
- Demographic data will be recorded.
- Information on medical history will be recorded based on review of the medical records and interview of the subject.
- Information on concomitant medication will be recorded.
- Physical examination, including body weight and height, will be performed.
- Vital signs (blood pressure and heart rate) will be measured.
- Blood samples will be drawn for analysis of haematology, clinical chemistry (including serum sodium) and coagulation factors.
- Urine samples will be collected for urinalysis.
- Serum and urine pregnancy tests will be performed in all pre- and perimenopausal female subjects.
- Assessment of OSA.
- 12-lead electrocardiogram (ECG) will be measured.
- The e-Diary will be dispensed. Subjects will be trained to complete the e-Diary and will be encouraged to complete the diary at home during 5 days for training purposes.
- The subject will be given instructions about lifestyle changes and will be requested to maintain these lifestyle changes throughout the trial (Section 4.3.3).

The e-Diary training will be followed by the trial site personnel (via the web-portal).

Prior to Visit 2 the subject will be reminded to complete the e-Diary (Section 7.1.1) for 3 consecutive days just prior to the visit.

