6.3 Visit 2 Active Run-in Period

All assessments and procedures to be performed at Visit 2 are listed below.

- The subject will complete the questionnaire (ISI), in the e-Diary (Section 7.1.1.3.2), at the trial site before any consultation with the trial site personnel takes place.
- Inclusion and exclusion criteria will be evaluated.
- Body weight will be measured.
- Vital signs (blood pressure and heart rate) will be measured.
- The subject will be interviewed about any changes in concomitant medication and about any adverse events since the last visit.
- Blood samples will be drawn for assessment of copeptin.
- The subject will be reminded about lifestyle changes (Section 4.3.3).
- Instructions for start and use of IMP will be given.
- IMP will be dispensed to eligible subjects for the 1-week active run-in (Table 5-1).

Prior to Visit 3 the subject will be reminded to complete the e-Diary (Section 7.1.1) for 3 consecutive days prior to the visit. The e-Diary will be reviewed for completeness (via the web-portal) by the trial site personnel.

Four days after the planned start of IMP treatment the subject will be telephoned to follow-up on safety.

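### No pregnancy test is scheduled at Visit 2, when the 500 µg run-in drug is first dispensed; the latest scheduled result is from Visit 1, nominally 14 days earlier

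*Protocol*

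**What the plan says.** The places that set the pregnancy-test schedule agree with one another.

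- **Protocol 7.2.6** places serum tests "at screening (Visit 1), Visit 4 and at the end-of-trial visit (Visit 8") and continues: "A urine pregnancy test will also be performed at screening (Visit 1").
- **Table 6-1** has a row "Pregnancy test - urine" marked at Visit 1 only, and a serum row marked at three visits.
- **Section 6.2 (Visit 1)**: "Serum and urine pregnancy tests will be performed in all pre- and perimenopausal female subjects".
- **Section 6.3 (Visit 2)** lists the ISI, eligibility review, weight, vital signs, concomitant medication and adverse events, a copeptin sample and lifestyle reminders. Then: "IMP will be dispensed to eligible subjects for the 1-week active run-in". It lists no pregnancy test.
- **Section 5.6.1**: "The IMP for the active run-in will only be dispensed to subjects who meet the eligibility criteria at Visit 2".
- **Section 4.1.2** makes a screening failure of "Any subject meeting one or more of the following exclusion criteria between Visit 1 (screening) through Visit 4 (randomisation"). Criterion 21 reads "Pregnancy, breastfeeding, or a planning to become pregnant during the period of the trial".

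The documents' one re-test rule for a long interval between Visits 1 and 2 is in the Table 6-1 footnotes and Section 7.1.3.1. If more than 21 days pass, serum sodium is measured again before Visit 2. Pregnancy testing has no such rule.

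**The concern.** Pregnancy is an exclusion criterion that has to hold at Visit 2 for run-in drug to be dispensed, yet no test is scheduled that day to inform the decision. The investigator reviews eligibility on a Visit 1 result. The plan foresees that the interval can stretch past 21 days and treats an older sodium value as stale, but gives the pregnancy result no equivalent limit.

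A pregnancy too early to detect at Visit 1, or conceived soon after it, could therefore be exposed to the whole run-in, about seven nightly doses of 500 µg, before the Visit 4 test. The stop rule in Section 8.4 works only once the pregnancy is known. What is at stake is avoidable exposure of a few women at most; nothing in the estimation or decision rules depends on it.

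**Working it through.** This is schedule arithmetic; no power or error-rate formula applies.

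**Inputs**
- Pre-randomisation period: 4 weeks = 28 days (3.5.1).
- Visit 2: Day -14; randomisation (Visit 4): Day 1, about 14 days later (Table 6-1).
- Run-in: 1 week of nightly dosing (5.1), so about 7 × 1 = 7 doses of 500 µg.
- Scheduled tests: Visits 1, 4 and 8 (7.2.6).

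**The plan's own figure.** Visit 1 to Visit 2 = 28 − 14 = 14 days, which matches the stated 2-week screening and lifestyle period.

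**Age of the latest scheduled result.** At dose *k*, age = (days from latest test to Visit 2) + (*k* − 1).

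| | First dose | Seventh dose |
|---|---|---|
| Current schedule, 14-day gap | 14 + 0 = 14 days | 14 + 6 = 20 days |
| Current schedule, gap over 21 days | more than 21 days | more than 21 + 6 = 27 days |
| Urine test at Visit 2, any gap | 0 days | 6 days |

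**Interval between scheduled tests before randomisation.** Now: 14 + 14 = about 28 days (Visit 1 to Visit 4). With a Visit 2 test: about 14 days, then about 14 days.

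**What a Visit 2 test could catch.** The documents give no detection lag. As an assumption, let a urine test turn positive *L* = 10 to 14 days after conception. The latest conception detectable at Visit 2, counted in days after Visit 1, is gap − *L*:
- 14-day gap: 14 − 14 = 0 to 14 − 10 = 4 days after Visit 1.
- 21-day gap: 21 − 14 = 7 to 21 − 10 = 11 days after Visit 1.

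On the planned schedule the extra yield is therefore mostly pregnancies that already existed at Visit 1 but were too early to show. Later conceptions are missed with or without the change.

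**The case against.** The strongest reply is that this is a consistent and deliberate choice. The visit lists, the flow chart and 7.2.6 agree, and 7.1.3 requires the Visit 1 laboratory reports to be available for judging eligibility before the run-in. Using screening results for run-in entry is thus the stated plan, and nothing in the documents demands a test on the day of dispensing. This stands: the point is a possible improvement, not a contradiction.

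The other controls are also real:
- two tests at Visit 1;
- documented contraception throughout (4.3.4);
- exclusion of women planning pregnancy;
- eligibility review at Visit 2;
- a safety call about four days into the run-in;
- the immediate stop in 8.4.

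The protocol also accepts about 12 weeks of nightly dosing between the Visit 4 and Visit 8 tests, at doses up to the same 500 µg, relying on contraception rather than frequent testing. That puts a 14-day gap in proportion. It does not remove the separate purpose of a test before first exposure, which is to keep an already pregnant woman from starting.

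Two stronger readings are not supported. A reader might infer that the protocol lets a woman be randomised and given drug at Visit 4 whatever her pregnancy result. It does not: 4.1.2 applies the exclusion through Visit 4, 5.6.1 limits randomised drug to subjects eligible then, and 6.5 lists the serum test before randomisation and dispensing. A reader might also infer a known fetal hazard. The protocol states no embryo-fetal hazard for FE 201836, and the Investigator's Brochure is not among the documents.

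**Conclusion.** The point holds as a minor subject-safety improvement to consider. All subjects who enter the run-in start 500 µg with no scheduled pregnancy test since Visit 1: nominally 14 days, with no stated upper limit for the pregnancy test. Adding a Visit 2 result takes the age at first dose to 0 days and halves the longest pre-randomisation interval between tests, from about 28 to about 14 days.

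The gain is small, and the change narrows the gap without closing it. How much it catches depends on the assumed 10 to 14 day detection lag. The documents do not give the number of pre- and perimenopausal women who will enter the run-in, so neither the number affected nor the risk can be estimated. No endpoint, analysis, power or error rate changes.

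**What to change.** Move the existing Visit 1 urine test to Visit 2, with matching edits in 6.2, 6.3, 7.2.6 and Table 6-1. Section 6.3 could add: *Every pre- or perimenopausal woman has a urine pregnancy test, read on site; run-in IMP is dispensed only after a negative result.* Section 7.3 needs a matching exception, because it sends all samples to central laboratories and allows local analysis only for serum sodium. Keep the serum tests at Visits 1, 4 and 8.

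**Cost.** A text and flow-chart amendment, and one urine sample at Visit 2, where urinalysis is not scheduled. The duplicate urine test at Visit 1 is lost, but the Visit 1 serum test remains. There is no net extra test, visit or blood draw.

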7.2.7 Electrocardiogram

A 12-lead ECG will be performed by the investigator or appropriate designee at the screening visit (Visit 1) and at the end-of-trial visit (Visit 8). The ECG should be taken after resting for 5 minutes. The ECG print-out should be reviewed, signed and dated by the investigator. Any abnormal, clinically significant changes should be reported as adverse events.

7.3 Handling of Biological Samples

A trial-specific laboratory manual will be provided to the participating sites, describing in detail how to handle, store and transport the biological samples in this trial. All biological samples will be analysed at central laboratories and will be destroyed after the results are available. For all biological samples collected in the trial, analyses beyond those described in the protocol can only be performed after obtaining the required approvals. The processes related to handling biological samples will be described in the informed consent documents and data protection legislation including local legislation will be adhered to.

In addition to the central laboratory, a local laboratory may be used for analysis of serum sodium if a quick turn-around time of the result is needed (Section 7.1.3.1).

8 ADVERSE EVENTS

8.1 Adverse Event Definition

An adverse event is any untoward medical occurrence in a subject participating in a clinical trial. It includes:

- Any unfavourable and unintended sign, symptom or disease temporally associated with the use of the IMP, whether or not considered to be caused by the IMP.
- Adverse events commonly observed and adverse events anticipated based on the pharmacological effect of the IMP.
- Any laboratory abnormality, vital sign or finding from physical examination assessed as clinically significant by the investigator (note: pre-existing conditions diagnosed through assessments and examinations at the screening visit or during the screening period are not adverse events, but are recorded as medical history).
- Accidental injuries, reasons for any change in medication (drug and/or dose), reasons for any medical, nursing or pharmacy consultation, or reasons for admission to hospital or surgical procedures.
- Overdoses and medication errors with and without clinical consequences.

